6.4. Will any assumptions for statistical methods be checked?

Normality will be assessed by visual inspection of histograms and q-q plots. Continuous baseline variables judged to follow a non-normal distribution will be summarized using medians and interquartile ranges. Right skewed continuous baseline variables will be transformed using a natural logarithm (base e) for high kurtosis, square-root for normal kurtosis and inverse transformation for low kurtosis before linear regression is performed. For the Cox proportional hazards regression model we will test the proportional hazard assumption using visual inspection. In case of violation of this assumption we will stratify for subgroups.

6.5. Will sensitivity analyses be performed?

We will perform best-case (last observation carried forward) and worst-case (assuming that all lost to follow up patients have recurrent HGAIN) scenarios for missing data to assess what might happen in case of violation of the assumption in survival analysis that patients with missing end-points have the same probability of recurrence during the remainder of the survival period as the other non-recurrent patients at the moment of loss-to-follow-up.

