3.2. Will randomization be performed in this study?

Patients were randomised (randomisation ratio 1:1) to be vaccinated 3 times with the qHPV vaccine (Gardasil®) or matching placebo at months 0, 2 and 6.

An independent central randomisation, ALEA Clinical software version 16 (FormsVision, Abcoude, The Netherlands) was used for computer generated tables per centre to allocate treatment. Randomisation was stratified for complete response versus partial response (from HG AIN to LG AIN) of the initial HG AIN lesion, for treatment less than 6 months ago versus treatment 6 months and longer ago, and for AMC versus other hospitals.

In this study the patients and treating physicians were blinded to treatment allocation. Blinding was maintained because the randomisation, preparation and delivery of the allocated medication (qHPV vaccine or placebo) was performed by an independent pharmacist.

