3.3. How was the sample size calculated?

The total sample size for the RCT was estimated to be 125 patients based on the following assumptions:

- Expected recurrence rate was 50% within 12 months in this study population. This recurrence rate was observed in our earlier studies (1, 2).
- In a previous non-concurrent cohort study qHPV (quadrivalent human papilloma virus) vaccination significantly (HR 0.50) reduced HG AIN recurrence rate among MSM successfully treated for AIN. (3)
- A superiority test will be performed to test a 50% relative reduction in recurrence rate. However, a 25% absolute reduction is also considered clinically relevant.
- A two group (not for continuity corrected) chi-square test with a 0,05 two-sided significance level will have 80% power to detect the difference between a recurrence rate of 50% in the placebo group and 25% in the vaccination group when the sample size in each group is 58.
- 5% drop out in both groups.

1. Richel O, de Vries HJ, van Noesel CJ, Dijkgraaf MG, Prins JM. Comparison of imiquimod, topical fluorouracil, and electrocautery for the treatment of anal intraepithelial neoplasia in HIV-positive men who have sex with men: an open-label, randomised controlled trial. *Lancet Oncol.* 2013 Mar 14. S1470-2045(13) 70067-6.

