3.6. When will the final statistical analysis of the study data be performed?

The statistical analysis of the primary outcome and all secondary outcomes will be performed after the follow-up of the last patient is completed and after all data is entered in the database, followed by data cleaning and locking of the database. It is expected that this will happen six months after the follow-up of the final patient in the study is completed, meaning that we expect that the statistical analyses will be performed in September and October 2019.

3.7. At which time points are the outcomes measured and which “windows” are allowed?

Screening for recurrent AIN was performed at screening (before the first vaccination) and at last vaccination (follow-up 6 months), and repeated at 6 (follow-up 12 months) and 12 months (follow-up 18 months) after the last vaccination. In case of recurrent high grade lesions patients reached the study end point, further follow-up was ceased and patients were referred to the regular AIN care for further treatment.

At the last follow up (18 months), an anal papsmear (cytology) was performed in order to rule out missing HGAIN recurrences by high-resolution anoscopy. In case the cytology indicated HSIL (high grade squamous intraepithelial lesion), high-resolution anoscopy was repeated (re-HRA).

In case of recurrence at the 6 month visit (third vaccination and first follow up), the venous blood samples to assess the HPV type-specific antibody response was still drawn 3 months afterwards.

All visits, except the baseline visit, had a visit window of two weeks before and two weeks after the nominal time points. The window for the re-HRA was preferably within 22 months after first vaccination.

Section 4. Statistical Principles.

4.1. Which level or levels of statistical significance will be used in the study?

Primary and secondary outcomes will be viewed as significantly different between qHPV vaccination and placebo group if the two-sided p-values are less than 0.05.

4.2. Will the analysis adjust for multiplicity of statistical testing to ensure control of type I error rate?

As there is one primary outcome measured at a single time point in this study, the analysis will not adjust for multiplicity of statistical testing.

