5.2. What are the inclusion and exclusion criteria for the study?

Inclusion criteria

In order to be eligible to participate in this study, a subject had to meet all of the following criteria:

- Written informed consent.
- Age \geq 18 years.
- HIV+ MSM, CD4 count $>$ 350/ul (maximum 6 months before screening visit).
- Biopsy-proven intra-anal high-grade AIN successfully treated in the past year with cauterization, cryotherapy, Efudix, imiquimod or another form of local treatment. A maximum interval of 1 year between last treatment and first vaccination is allowed. Lesions with regression from HG to LG AIN (AIN 1) will also be eligible.
- Lesions (still) in remission.
 - Remission has to be established by 2 independent HRA anoscopists.
 - A maximum interval of 3 months is allowed between the first of these HRAs and the first vaccination, and a maximum interval of 6 weeks is allowed between the second of these HRAs and the first vaccination.
 - Biopsies of suspect lesions need to be obtained in one of the HRA sessions.
- Good performance status (a Karnofsky performance score of \geq 60 [on a scale of 0 to 100, with higher scores indicating better performance status]).
- Pre-treatment haematology, and plasma ASAT, ALAT and creatinine levels compatible with study inclusion (maximum 6 weeks before screening visit).

Exclusion criteria

In order to be non-eligible to participate in this study, a subject had to meet at least one of the following criteria:

- Immunosuppressive medication or other diseases associated with immunodeficiency.
- Life expectancy less than one year.
- Previous HPV vaccination.
- History of anal cancer.
- Other diseases not compatible with study participation.
- Allergy against constituent of Gardasil ® vaccine.
- Currently peri-anal AIN2 or 3.

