5.3. Which information will be presented in the flow chart for this study?

The mock-up of the CONSORT flow diagram is presented in the appendix to this statistical analysis plan.

5.4. What is the expected level of, timing of and reasons for withdrawal from the intervention and/or from follow-up and how will this be presented in the study reports?

We expect 5% of patients to have been lost to follow-up or dropped out of the study before assessment of the primary outcome was complete. We replaced patients who did not receive all 3 vaccines, but according to the study protocol these patients remained in follow-up. We will report the number and percentage of patients in each study arm who: stopped receiving vaccinations before having received all 3 vaccines; or dropped out before assessment of the primary outcome was complete. For the drop out patients, we will present line listings of the reasons for withdrawal or loss to follow-up.

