A logistic regression model with treatment arm on recurrence of intra-anal or peri-anal HG AIN will be performed, correcting for the stratification factors 'treatment centre group', 'complete or partial response (from HG AIN to LG AIN) of the initial HG AIN' lesion and 'treatment less or equal/more than 6 months ago'. In a second step, a maximum of two baseline variables most predictive (if any) of recurrence will be added to the model. Adjusted odds ratios with 95% confidence interval will be reported.

In case of missing end-point data on recurrence, the two groups for the ITT analysis will be compared using Kaplan-Meier survival (or life tables if more appropriate) analysis. The difference between the fractions free of recurrence at 6, 12 and 18 months since inclusion will be assessed for statistical significance based on the widths of the corresponding confidence intervals. Additionally, we will perform best-case (last observation carried forward) and worst-case (assuming that all lost to follow up patients have recurrent HGAIN) scenarios for missing data to assess what might happen in case of violation of the assumption in survival analysis that patients with missing end-points have the same probability of recurrence during the remainder of the survival period as the other non-recurrent patients at the moment of loss-to-follow-up.

A Cox proportional hazards regression model with treatment arm on the time to recurrence of intra-anal or peri-anal HG AIN will be performed, correcting for the stratification factors 'treatment centre group', 'complete or partial response (from HG AIN to LG AIN) of the initial HG AIN' lesion and 'treatment less or equal/more than 6 months ago' as well as for up to two other baseline variables most predictive (if any) of recurrence. The effect sizes from this model will be expressed as an adjusted hazard ratio with 95% confidence interval. In addition, the survival time will be compared in the intention to treat, as treated, and per protocol populations using a log-rank test.

Secondary outcomes

The analysis of the secondary outcomes will only be performed in the intention-to-treat population and will be based on the t-test for continuous, normally distributed outcomes, the Mann-Whitney-U test for continuous, non-normally distributed outcomes.

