6.6. Will subgroup analyses be performed?

Subgroup analyses will be performed using logistic regression analysis with interaction terms for patients who had a complete response after initial treatment versus those with regression from HG to LG AIN on the one hand and for patients treated in the past 6 months versus those treated 6 months and longer ago on the other hand.

6.7. How will missing data be reported in the study reports and handled in the statistical analysis?

Missing data will be reported descriptively.
In case of missing end-point data on recurrence for the primary outcome, the two groups for the ITT analysis will be compared using Kaplan-Meier survival (or life tables if more appropriate) analysis. The difference between the fractions free of recurrence at 18 months since inclusion will be assessed for statistical significance based on the widths of the corresponding confidence intervals. Additionally, we will perform best-case and worst-case scenarios for missing data to assess what might happen in case of violation of the assumption in survival analysis that patients with missing end-points have the same probability of recurrence during the remainder of the survival period as the other non-recurrent patients at the moment of loss-to-follow-up.

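### The planned best-case and worst-case scenarios give lost patients the same outcome in both arms, so they do not bound the vaccine-placebo difference

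*SAP*

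**What the plan says.** - SAP 6.5 plans "best-case (last observation carried forward) and worst-case (assuming that all lost to follow up patients have recurrent HGAIN) scenarios for missing data". SAP 6.3 defines the pair in the same way: "best-case (last observation carried forward) and worst-case (assuming that all lost to follow up patients have recurrent HGAIN) scenarios". SAP 6.7 repeats the labels without defining them: "Additionally, we will perform best-case and worst-case scenarios for missing data to assess what might happen in case of violation of the assumption". The stated aim is to probe the survival-analysis assumption that lost patients would have recurred at the same rate as recurrence-free patients still under observation. None of the three sections assigns outcomes by arm.
- SAP 5.2 requires at entry: "Lesions (still) in remission". SAP 3.7 adds: "In case of recurrent high grade lesions patients reached the study end point, further follow-up was ceased".
- SAP 3.2 gives "randomisation ratio 1:1", and SAP 3.3 assumes "5% drop out in both groups".
- SAP 6.3 tests the primary outcome with a chi-square test and presents the absolute difference in proportions with its 95% confidence interval. SAP 6.8 plans no further analyses of the primary or secondary outcomes.
- On drop-outs, SAP 5.4 says: "We will report the number and percentage of patients in each study arm who" stopped vaccination early or left before the primary outcome was complete.

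**The concern.** Taken together, the entry criterion and the stopping of follow-up at recurrence mean that anyone lost was recurrence-free when last seen. Last observation carried forward therefore codes every lost patient as free of recurrence, whichever arm he is in, and the worst case codes every lost patient as recurrent, again in both arms. The two scenarios move the arms in the same direction.

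The trial's question is the difference between the arms. Missing outcomes bias that difference most when lost vaccine patients and lost placebo patients fare differently, and no planned scenario represents this. The Kaplan-Meier, log-rank and Cox analyses do not fill the gap, because they rely on the censoring assumption that the scenarios are meant to probe.

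The risk is one of reporting. A result that is significant under both the best and the worst case would naturally be described as robust to missing data, although the pattern of loss most able to overturn it was never examined.

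**Working it through.** **Inputs.** From the SAP: recurrence 50% v 25%, uncorrected chi-square, two-sided 0.05, 80% power, 58 per group, 5% drop-out in both groups, total 125 (3.3); allocation 1:1 (3.2). Assumed: 62 randomised per arm, 3 lost per arm (3/62 = 4.8%), the observed recurrence counts used below, and the uncorrected chi-square for the scenario tables. The SAP names no test for the scenarios and gives no results.

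**Plan's own figure.** n = [1.960·√(2·0.375·0.625) + 0.842·√(0.5·0.5 + 0.25·0.75)]² / 0.25² = 57.7, so 58 per group, as stated. Allowing for 5% loss, 58/0.95 = 61.1, so 62 per arm, in line with the stated total of 125.

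**Algebra.** Let x be observed recurrences, m patients lost and n patients randomised, with subscripts p (placebo) and v (vaccine). Under the planned scenarios

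difference = (x_p/n_p − x_v/n_v) + c·(m_p/n_p − m_v/n_v), with c = 0 (best) or 1 (worst).

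With equal loss fractions the second term is zero. The full range of the difference runs from x_p/n_p − (x_v + m_v)/n_v to (x_p + m_p)/n_p − x_v/n_v. Its width is m_p/n_p + m_v/n_v = 3/62 + 3/62 = 9.7 points.

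**Scenario tables** (n = 62 per arm, 3 lost per arm; counts are placebo v vaccine recurrences; adverse means lost vaccine patients recur and lost placebo patients do not):

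| Observed | Best case | Worst case | Adverse |
|---|---|---|---|
| 30 v 15 | 30 v 15: 24.2 points, p=0.005 | 33 v 18: 24.2 points, p=0.006 | 30 v 18: 19.4 points, p=0.027 |
| 30 v 17 | 30 v 17: 21.0 points, p=0.016 | 33 v 20: 21.0 points, p=0.018 | 30 v 20: 16.1 points, p=0.067 |
| 29 v 18 | 29 v 18: 17.7 points, p=0.042 | 32 v 21: 17.7 points, p=0.046 | 29 v 21: 12.9 points, p=0.14 |

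**Tipping point** (number of lost vaccine patients who must recur, with no lost placebo patient recurring, for p to reach 0.05):

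- 30 v 15: 5 (p=0.043 at 4, 0.067 at 5), more than the 3 lost.
- 30 v 17: 3 (p=0.043 at 2, 0.067 at 3).
- 29 v 18: 1 (p=0.065).

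**Unequal loss** (1 placebo, 5 vaccine; 30 v 18 observed). Best case 30 v 18: 19.4 points, p=0.027. Worst case 31 v 23: 12.9 points, p=0.147. Here the pair does show a change in significance, but the bounds are 11.3 points (30 v 23) and 21.0 points (31 v 18). The pair equals the bounds only if every loss falls in one arm.

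**Heavier loss** (62 vaccine, 63 placebo, 6 lost in each; observed 14/56 vaccine, 28/57 placebo). Planned pair: 21.9 and 21.7 points, p=0.010 and 0.014. Adverse case, 20/62 v 28/63: 12.2 points, p=0.161.

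**How often it could matter.** Exact enumeration with independent binomials (59 observed and 3 lost per arm, placebo rate 50%, vaccine rate 25%) gives 80% of trials significant in both planned scenarios. Of those, 24.8% lose significance in the adverse table. The share is 12.8% at a vaccine rate of 20% and 37.7% at 30%. At 50% v 25% it is 6.5% with 1 lost per arm and 14.8% with 2.

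**The case against.** The SAP defines both scenarios openly and nowhere claims that they bound the treatment difference. None recurring and all recurring are the two extremes of the assumption it sets out to probe. At the design rates with 5% loss, even the adverse case stays significant. The adverse case is also improbable: if lost patients follow the design rates, the chance that all 3 lost vaccine patients recur and none of the 3 lost placebo patients do is 0.25³ × 0.5³ = 0.2%, and at 50% in both arms it is 0.5⁶ = 1.6%. Patients and treating physicians are blinded, which makes loss related to both arm and outcome less likely. Drop-outs are reported per arm, so a reader could build the missing tables. The p-values also depend on a chi-square test that the SAP does not assign to these scenarios.

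Much of this stands, and it limits the size of the point. The enumeration shares are conditional on the most extreme assignment and are not probabilities of a wrong conclusion. What remains is that the aim is to see what happens if loss is informative, and the planned pair leaves out the form of informative loss that most affects the comparison. The near-constancy of the difference under equal loss follows from algebra and does not depend on the test. Bounds that a reader derives afterwards are not prespecified.

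**Conclusion.** The concern holds as a cheap improvement that should be made. The planned pair is coherent but incomplete. Under the SAP's own expectation of 1:1 allocation and equal 5% loss, it leaves the risk difference unchanged (by under 0.1 point with 62 and 63 patients), while the range compatible with the missing data is about 10 points wide. A result near the design rates with 5% loss would survive the adverse case. A moderately significant or borderline result, or one with about 10% loss, could pass both planned scenarios and fail the adverse one. The algebra rests on the SAP alone; the p-values rest on the assumed counts, losses and uncorrected chi-square test.

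**What to change.** In SAP 6.3, 6.5 and 6.7, add two arm-specific scenarios: lost vaccine patients recurrent with lost placebo patients recurrence-free, and the reverse. Keep the existing pair, described as same-direction cases (all lost patients non-recurrent, all recurrent). Name the test and interval used for all four. If the conclusion changes in any of them, report the tipping point: the number of lost vaccine patients who would have to recur.

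The cost is two more 2×2 tables and one sentence in the SAP, with no new data. The downside is a wider reported range from deliberately extreme scenarios, which the report should label as such. The SAP is dated 18-10-2019 and deblinding was planned for mid-October 2019, so the addition counts as prespecified only if made before deblinding; otherwise it should be reported as post hoc.

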6.6. Will subgroup analyses be performed?

Subgroup analyses will be performed using logistic regression analysis with interaction terms for patients who had a complete response after initial treatment versus those with regression from HG to LG AIN on the one hand and for patients treated in the past 6 months versus those treated 6 months and longer ago on the other hand.

6.7. How will missing data be reported in the study reports and handled in the statistical analysis?

Missing data will be reported descriptively.
In case of missing end-point data on recurrence for the primary outcome, the two groups for the ITT analysis will be compared using Kaplan-Meier survival (or life tables if more appropriate) analysis. The difference between the fractions free of recurrence at 18 months since inclusion will be assessed for statistical significance based on the widths of the corresponding confidence intervals. Additionally, we will perform best-case and worst-case scenarios for missing data to assess what might happen in case of violation of the assumption in survival analysis that patients with missing end-points have the same probability of recurrence during the remainder of the survival period as the other non-recurrent patients at the moment of loss-to-follow-up.

6.8. Will additional analyses on the primary or secondary outcomes be performed?

No additional analyses will be performed on the primary or secondary outcomes.

6.9. How will harms be reported?

We will present line listings of safety outcomes. Adverse events will be graded according to version 4.0 of the Common Terminology Criteria for Adverse Events (CTCAE), which grades events on a scale of 1 to 5, with higher grades indicating greater severity. Safety outcomes will be classified by the clinical research coordinators as: expected complications of qHPV vaccination; suspected unexpected serious adverse drug reactions; and other (serious) adverse events. Each class of safety outcome will be presented using tabulations of counts and percentages of events and of patients experiencing one or more of each type of event for each treatment arm. Adverse effects will be reported using descriptive statistics. No formal statistical testing will be performed.

6.10. Which statistical software will be used to carry out the statistical analyses?

All statistical analysis will be performed in IBM SPSS Statistics for Windows, Version 25.0 (IBM Corp, Armonk, NY).

Section 7. References to literature, standard operating procedures and reporting guidelines.

7.1. Are non-standard statistical procedures to be used, which have not been described in sufficient depth in the previous sections?

Not applicable.

7.2. What is the title, date and version number of the current data management plan?

The current data management plan has the title "Data management plan for the VACCAIN-P study", version number 1.0, is dated 22-10-2019 and is stored in the trial master file.

7.3. What is the title, date and version number of the current data validation and derivation plan?

Data validation and derivation is implemented in the database program Research Online as documented in the Data Management Plan of Research Online and is stored in the trial master file.

7.4. What is the title, date and version number of the current study master file and where it is stored?

The trial master file has the title "Trial master file for the VACCAIN-P study", is last updated at 9-9-2019 and is stored on paper at room A0-226 at the Amsterdam University Medical Center, location AMC, Amsterdam.

7.5. Where are the syntax files for data extraction, manipulation and preparation and statistical analysis stored?

The syntax files for data extraction, manipulation and preparation and statistical analysis will be stored at the location *G:\diva\Dermatologie\AIN en proctologie\Overige bestanden niet voor fotografie\VACCAIN-P studie\Statistical Master File.*

7.6. Which standard operating procedures will be adhered to when using and analysing data from this study?

When using and analysing data from the VACCAIN-P study, researchers will adhere to the standard operating procedure AMC RDM001 Research data management.

